2.0 Research Design Overview

GET PrEPD-Psychiatry is a mixed-methods, developmental study to adapt an SDM intervention to be specific for psychiatry decisions (Aim 1, IRB #1807699331), evaluate its feasibility and acceptability (Aim 2), and examine potential mechanisms of change and preliminary outcomes (Aim 3) of this innovative intervention to increase SDM and self-management for adults with SMI. In line with NIMH priorities, we are examining whether GET PrEPD-Psychiatry engages the target mechanisms that putatively underlie the intervention (i.e., patient activation and communication self-efficacy; Aim 3). For Aim 1, we used approximately 200 transcripts from our prior study of SDM in psychiatry to cull language used in decision-making. These conversations were used to program the Virtual Provider to represent common interactions and decisions in psychiatric visits. We iteratively tested the use of the Virtual Provider program with patients and obtained feedback from our psychiatry consultants to refine the program. For Aim 2, we will recruit up to 40 patients to participate in GET PrEPD-Psychiatry (4 approximately weekly goal setting/coaching sessions, coupled with Virtual Provider program training and practice). We will assess participant satisfaction and utility ratings, as well as track their use (frequency and time-on-task) of the Virtual Provider program. For Aim 3, we will follow enrolled patient participants to interview them. **We hypothesize that participants will have significantly 1) improved**

mechanisms of change, demonstrated by increases in self-reported activation and communication self-efficacy, 2) improved SDM, and 3) improved self-management and recovery attitudes.

While we hypothesize that this intervention will increase self-reported activation and communication self-efficacy, improve SDM, and improve self-management and recovery attitudes, there is no evidence to suggest that the intervention may cause worsening of these. There is the possibility that there will be no change. In [name] COOPERATE study in which Drs. [name], [name], and [name] are co-investigators (IRB #1712397218), a similar coaching intervention is used; 76 subjects have completed the intervention so far. There have been no risks identified to suggest the intervention is associated with negative outcomes for subjects. Potential risks of the study include feeling uncomfortable, nervous, or anxious, as well as the risk of loss of confidentiality.

3.0 Setting, Recruitment, and Enrollment

We will recruit up to 40 patients at the Sandra Eskenazi Mental Health Center (SEMHC, formerly Midtown Mental Health Center) who are being seen in outpatient services for adults with SMI. In our prior study with these teams, over half of participating consumers were male (56.9%) and African American (54.8%). Most participants were diagnosed with schizophrenia (67.6%); other frequent diagnoses included bipolar disorder and major depression. Following procedures established in our CommonGround study ³³ and our earlier pilot study on patient activation,⁸¹ we will recruit patients in the clinic, as they check in for a visit. The receptionist or other clinic staff will notify patients of an opportunity to learn more about the study and may distribute brief information about the study (recruitment flyer). Recruitment flyers may also be posted or distributed to potential subjects. If interested, patients will be referred to the RA or to call the phone number on the recruitment flyer with any questions or to find out more information. RAs will be stationed in the waiting area on specific, pre-determined days and be available to describe the study, complete informed consent, complete a baseline interview, and attempt to audio-record the visit with prescribers who have already given consent to participate. There may be times audio-recording the prescriber visit is not feasible (e.g., subject eligibility not complete prior to appointment time with prescriber or the prescriber has not provided consent). Following the initial visit, we will complete the first session of the intervention or, if needed, arrange a time for this session to be completed within approximately 10 days. Because the treatment teams serve people with SMI who may have more difficulties in patient activation and SDM skills, we will be able to test feasibility and acceptability with people who experience a range of difficulties. The follow-up measures can occur any time after coaching session 4, within about 3 months of baseline. Audio-recording of the psychiatry visit with consented prescribers will take place approximately 3 months after baseline – based on clinic flow, we expect this will be the next available clinic visit after completion of the intervention, but this could vary somewhat for individual patients. Participants will be paid \$25 for each research assessment visit completed (baseline and 3 months), for a total of \$50 per participant.

4.0 Eligibility Criteria

Providers:

Must be a prescribing provider (e.g., psychiatrist, nurse practitioner providing psychiatric care) at SEMHC who provides care to adult outpatients

Patients:

Inclusion Criteria

- At least 18 years of age
- Current outpatient receiving mental health care at SEMHC
- English speaking
- Willing to participate in 4 approximately weekly coaching sessions, engage in practice with the Virtual Provider Program, allow prescriber appointments (if prescriber has provided consent) and coaching sessions to be audio recorded*

Exclusion Criteria

- No reasonable access to the internet on a computer
- Inability or unwillingness to use a computer (necessary for Virtual Provider Program practice)
- Never or rarely uses a computer or similar device (based on self-report)
- Very or somewhat uncomfortable using a computer or similar device (based on self-report)

*Research assistants will always ask permission prior to beginning audio recording and subject can refuse individual audio recording events and continue participation in the study.

4.0 Outcome Measures, Training, Fidelity

We will measure each component of our model, with the exception of observed SDM, (Figure 2 and Table 2) in addition to demographics and chart-reported diagnoses. We chose brief validated measures for low participant burden. Aside from Feasibility (Aim 2) and SDM ratings (Aim 3), the remaining measures are self-report. Acceptability (Aim 2) is only measured after the intervention, and all others are administered at both baseline and 3 months. From each enrolled subject's medical record, we will collect recent primary and secondary mental health diagnoses made by a prescriber (or other mental health provider if prescriber diagnoses are not available) in relation to the baseline visit date.

Feasibility Assessment (Aim 2). Feasibility will be assessed by (1) tracking the number of participants who sign up for the intervention, and recording the number of people we invited in order to meet sample size goals and the reasons for declining; (2) tracking the number of enrolled participants who attend and complete the coaching sessions; and (3) tracking use of the online Virtual Provider program (which is accessible from any computer) via time-stamp data showing how frequently each participant accessed the online program and how much time they spent – during individual sessions and in total – using the program. In terms of benchmarks, the percentage of people who agree to enroll will inform the planning for our next study – a full-scale clinical trial – by allowing us to estimate the number of participants we need to engage in order to meet sample size goals for a fully powered trial.

Table 2. Measures

Aim	Construct	Measure	Items
2	Acceptability*	Narrative Evaluation of Intervention Interview (NEII)	16
3	Patient Activation	Patient Activation Measure for Mental Health (PAM-MH)	13
3	Patient Activation	Altarum Consumer Engagement (ACE) Measure	12
3	Communication Self-Efficacy	Perceived Efficacy in Patient-Provider Interactions (PEPPI-5)	5

Acceptability Assessment (Aim 2). In this open trial, we will assess participants' satisfaction with the training by asking them to complete the Narrative Evaluation of Intervention Interview¹⁰⁵ that we have used in other interventions with people with SMI.^{106,107} These questions will focus on participant feedback on the whole intervention as well as specific components that were most and least helpful to them (e.g., goal setting, coaching sessions, Virtual Provider).

3	Observed SDM**	SDM Scale, rated from audiotaped patient-provider visit	9
3	Self-management	Illness Management and Recovery Scale	15
3	Recovery attitudes	Recovery Assessment Scale (brief version)	20

*With the exception of acceptability completed at the follow-up visit, all measures will be given at baseline and 3-month follow-up.
**Audio recordings of prescriber appointments have not been feasible; therefore, changes in observed SDM will not be analyzed. (updated 1/21/2022)

Target Mechanisms (Aim 3). **Patient activation** will be measured with the 13-item Patient Activation Measure Short Form-Mental Health (PAM-MH),¹⁰⁸ which assesses patient knowledge, skill, and confidence for self-managing one's chronic health condition. The PAM-MH has shown good reliability ($\alpha = .87\text{-.88}$) and validity in many studies, including our own.^{81,108-111}

Communication self-efficacy will be measured with the Perceived Efficacy in Patient-Physician Interactions Scale (PEPPI-5), a 5-item scale that measures patients' self-efficacy in obtaining medical information and getting their most important health concern discussed in a clinic visit. The PEPPI-5 has demonstrated responsibility to interventions to activate adults with SMI.^{41,112} We will also use the Altarum Consumer Engagement (ACE) Measure that assesses commitment, informed choice, and navigation. Utilizing both of these measures of patient activation for this pilot test will inform our research to determine which may be the most viable measure for a larger controlled trial in the future.

Primary Outcome: SDM (Aim 3). To ascertain effects of GET PrEPD-Psychiatry on SDM, we attempted to audio-record each patient's baseline visit (prior to intervention) and the first visit available after the fourth and final coaching session for those who are patients of prescribers who provided consent; however, recording has proven to not be feasible for various reasons. Given this is a feasibility study and we have learned that collecting recordings this way is not feasible, we have still learned something important from the work we have done. We will no longer attempt to record these appointments.

Secondary Outcomes: Self-Management and Recovery (Aim 3). **Illness self-management** will be assessed with the consumer-rated Illness Management and Recovery Scale.¹¹⁴ Items are rated on a 5-point behaviorally anchored scale; the mean across all 15 items forms an overall score of illness management, with higher scores indicating better self-management. The IMR Scales have shown internal consistency, stability, sensitivity to change over time, and correlations with indices of functioning, symptoms, and recovery.¹¹⁵⁻¹¹⁷

Recovery attitudes will be assessed using the total score of the Brief version of the Recovery Assessment Scale.^{118,119} Respondents endorse 20 items (e.g., "I have a desire to succeed.") on a scale from 1 ("strongly disagree") to 5 ("strongly agree"). RAS total score has shown good test-retest reliability, internal consistency, and correlates with measures of self-esteem, empowerment, and quality of life.¹¹⁸

Training for Coaches. Clinical psychology doctoral students and/or staff with community mental health experience will serve as coaches. [name] will oversee training, which will consist of didactics, demonstrations, and role-plays developed by the research team based on prior experience. Intervention sessions will be audio-recorded; however, participants may, at times, decline audio recording an intervention session. A random subset of session recordings will be reviewed for fidelity and quality control. On those selected sessions, [name] will complete a coach adherence checklist to help guide feedback during weekly group supervision. Role-play will be used to reinforce and correct deviations from study procedures.

Treatment Fidelity. We will use treatment fidelity strategies consistent with the NIH Behavior Change Consortium recommendations.¹⁰⁴ Strategies will include: (1) using standardized intervention protocols and training; (2) monitoring audio-recorded intervention sessions; (3) using coach adherence checklists to track

protocol deviations; (4) using coach notes to document uptake of intervention; and (5) holding weekly study administration meetings to address problems or concerns.

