GET PrEPD-Psychiatry focuses on 4 communication skills: (1) agenda setting, (2) asking questions, (3) communicating goal context, and (4) discussing pros/cons of treatment options. Agenda setting skills help patients ensure their central goals, priorities, and preferences are discussed in the visit.^{49,50} Helping patients to formulate effective questions and engage providers in instructive dialogue about their concerns enables them to obtain tailored information and creates an atmosphere conducive to SDM.⁵¹ For example, by developing skills to communicate how treatment goals fit into their broader life context, patients are better equipped to elicit understanding and empathy from providers. Developing discussion skills (e.g., pros/cons) prepares patients to "hold their own" when negotiating treatment with providers and, ultimately, to make an informed, collaborative decision.⁵²

Skills Practice. Although interventions to enhance patient activation and communication exist in mental health,^{41,42} GET PrEPD-Psychiatry is innovative by allowing individualized, repeated practice of skills using the Virtual Human system. Patients practice these skills by interacting with 3D animated Virtual Providers who

display gestural and facial expressions that are triggered by patients' questions/statements (see Fig 3 for sample). To personalize the practice sessions, patients can select the gender and race of the Virtual Provider. Patients interact with Virtual Providers by selecting questions/statements from a menu (with the option of using a typed interface only in the "Questions about my treatment" category). Providing pre-populated choices is easier for users, especially patients with lower health literacy and who are less technologically-savvy, particularly during early stages of skill acquisition. Provider responses are transmitted with on-screen text, pre-recorded audio, and animations (non-verbal behavior). The system maintains a log of practice frequency/duration, which topics were selected and in what order for each patient (using assigned Research IDs), which allows for monitoring of progress (and subsequent troubleshooting during individual coaching sessions) and examining the relationship between amount of skills practice and our outcome measures. The system will also maintain a log of which Virtual Provider was chosen, if the Welcome Video was viewed, and the number of times the Help and Go Back to Main Page buttons were selected.

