Impact on Science, Practice, and the Field

This R34 is the next logical step in a program of research to help activate people with SMI to be more involved in treatment decisions as a critical part of self-management and recovery. The GET PrEPD-Psychiatry intervention builds on strengths of prior promising SDM interventions, while aiming to overcome key barriers of those approaches. The proposed project will result in a technologically advanced, ecologically-valid, and highly scalable approach to activating patients and enhancing their communication skills for participation in SDM. This project will also increase scientific knowledge by establishing feasibility and acceptability of this approach in community mental health settings. Importantly, we will also be examining proximal targets for the intervention – patient activation and communication self-efficacy – that can lead to better SDM, and ultimately to better recovery outcomes. These are critical steps before GET PrEPD-Psychiatry can be rigorously tested in a large, multi-site clinical trial. Ultimately, successful completion of our work will yield an innovative and scalable approach to addressing a critical issue for mental health services.

Figure 3.

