5.0 Study Calendar

	Screening	Baseline	Weekly Coaching Sessions 1-4	3-Month Follow-up^
Informed Consent and Authorization	X			
Eligibility Checklist	X			
Demographics, Contact Information	X			
PAM-MH		X		X
ACE Measure		X		X
PEPPI-5		X		X
IMR Scale		X		X
RAS		X		X
NEII				X
Intervention**			X	

[^]Activities can occur any time after coaching session 4, within approximately 3 months of Baseline.

*After completion of coaching intervention, ideally the first prescriber appointment that follows the intervention (time frame could vary).

**Practice with Virtual Provider Program will be encouraged through the end of the study.

We anticipate each subject's participation to last approximately 3-4 months; however, this is dependent on when their first prescriber appointment following the intervention takes place.

The goal is to complete 4 weekly coaching sessions with each subject and the first session taking place within approximately 10 days of baseline data collection. We recognize the need to be flexible with the remaining sessions and will allow coaching sessions 2-4 to take place up to approximately 14 days after the previous session barring extenuating circumstances.

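### Is the enrolment percentage meant for planning the full trial too loosely defined, with patients excluded on the computer criteria left uncounted?

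*Combined protocol and SAP*

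**What the plan says.** Section 4.0 Outcome Measures, Training, Fidelity (Feasibility Assessment, Aim 2) lists three things to track. The first is sign-ups, together with "recording the number of people we invited in order to meet sample size goals and the reasons for declining". The second is "tracking the number of enrolled participants who attend and complete the coaching sessions". The third is logged use of the Virtual Provider program. The paragraph then adds that "the percentage of people who agree to enroll will inform the planning for our next study", so that the number of people to engage in a full trial can be estimated. No target or threshold is attached to the percentage.

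Section 3.0 gives three routes to the study: reception or clinic staff mention it, flyers are posted or handed out, and research assistants in the waiting area describe it. The cap is 40 patients.

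Section 4.0 Eligibility Criteria has four patient exclusions. They cover internet access on a computer, ability and willingness to use one, frequency of use, and comfort, where even mild self-reported discomfort excludes. Section 5.0 Study Calendar places consent and the "Eligibility Checklist" in the same Screening column.

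**The concern.** The percentage has a job to do, and its terms are loose. Signing up, agreeing to enrol and being enrolled are not equated, and an invitation is not defined for the three routes. Section 3.0 also mentions "subject eligibility not complete prior to appointment time with prescriber", which suggests that a patient might agree before eligibility is settled. If such a patient is later ruled out but stays in the numerator, the next trial would plan too few invitations.

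The second strand is about whom the results describe. Every exclusion screens on computers, yet no listed feasibility measure counts those ruled out. Section 1.0 speaks of "establishing feasibility and acceptability of this approach in community mental health settings" and calls the menu format "easier for users, especially patients with lower health literacy and who are less technologically-savvy". Section 8.0 claims broad reach. Attendance and program use are seen only in patients who passed the computer criteria, and a reader might want to know what share that is.

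**Working it through.** **Inputs.** E = 40 enrolled (cap, Sections 2.0 and 3.0). Let I be the number invited, D the number who decline, S the sign-ups, and x the patients who agree but are then found ineligible. The paragraph plans to record I, S and reasons for declining. No document gives a value for I, D, S or x, or any enrolment percentage, so there is no stated figure to reproduce.

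**Two readings of the ratio.** Take I = E + D + x. Anyone ruled out before agreeing adds equally to both denominators and cancels from the comparison.

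- Enrolled over invited: E/I = 40/(40 + D + x)
- Agreed over invited: (E + x)/I = (40 + x)/(40 + D + x)
- Agreed-based rate divided by enrolled-based rate: (40 + x)/40 = 1 + x/40, whatever D is

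With D = 40 (assumed):

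| x (assumed) | Agreed/invited | Enrolled/invited | Factor |
|---|---|---|---|
| 0 | 40/80 = 50% | 40/80 = 50% | 1.0 |
| 10 | 50/90 = 56% | 40/90 = 44% | 1.25 |
| 20 | 60/100 = 60% | 40/100 = 40% | 1.5 |
| 40 | 80/120 = 67% | 40/120 = 33% | 2.0 |

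The last row supposes that half of those who agree (40 of 80) prove ineligible. The table shows that the ratios differ when x is above zero. It does not show that x is above zero here.

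**A third reading, eligible people only in the denominator.** If 50% of eligible people agree (assumed) and 10% to 50% of those approached are excluded (assumed), the yield among all approached is 0.5 × 0.9 = 45% down to 0.5 × 0.5 = 25%. Per 100 enrolled, that means approaching 223 to 400 people, against 100/0.5 = 200 on the eligible-only basis. The plan counts people invited, however, and nothing in it restricts the denominator to eligible people.

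**Do the planned counts settle it?** If sign-up means enrolled, then S = E and S/I is already the cautious ratio. If sign-up means agreed, then S = E + x, so x = S − E, and E/I is still available because attendance is tracked among the enrolled. Provided every decliner is logged as one, total ineligible is I − E − D. The split by criterion comes from the checklist.

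**Which reading does the text favour?** Invitations are counted in relation to filling the sample, which is invitations per place filled and therefore close to E/I. The remark about incomplete eligibility explains why a prescriber visit might go unrecorded. It does not say that agreement comes first, and the calendar gives no order within the Screening column. A positive x is possible but not shown.

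**What would an exclusion tally add?** If 20 of 100 screened were excluded, the share would be 20% (Wilson 95% interval 13% to 29%). If 0 of 80 were excluded, the upper limit would be 4.6%. Either figure describes only patients who reached screening. Those who passed by a flyer or ignored the receptionist have no checklist, so the tally could not tie attendance and use to the whole clinic population.

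**The case for a change.** The best case for a change is that Section 6.0 makes feasibility the purpose of the study, so recruitment yield is a main product and its formula should be written down. A posted flyer yields no countable invitation. Unwillingness to use a computer is an exclusion, but it could as easily be logged as a reason for declining, which blurs D and x. No sentence commits the team to tabulating exclusions. The remedy would cost two definitions and one tally from an existing form.

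The factual parts of this stand: the ratio is implied rather than stated, an invitation is not made operational, and the boundary between declining and ineligibility is soft. What does not follow is a wrong result. No rule in the plan tells anyone to count ineligible patients as enrolled. Conversation with a research assistant is the one contact point the study can count directly, and a pilot report would normally use it. Losses at the reception and flyer stage stay unknown under any definition. Recruitment was also under way by January 2022 (Section 3.0), so for patients already screened a new definition could draw only on checklists already completed.

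The reach argument is weaker. The menu remark explains a choice of interface. The wider statements in Sections 1.0 and 8.0 are grant framing, and no planned analysis extrapolates attendance or use beyond those enrolled. The computer criteria are stated openly, so a reader can see whom the results cover.

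**Conclusion.** No change to the plan. This is missing detail that analysts fill sensibly when they report participant flow: invited, declined with reasons, ineligible by criterion, enrolled. The numerator and denominator are both named, and the planned counts with the existing eligibility form are enough to compute enrolled over invited. On that reading the planning error is nil (factor 1.0). On the less natural reading it is 1 + x/40, where x is unknown and every value above zero used here is assumed. The conclusion rests on invitations, enrolments and declines being logged as the plan says, and on completed checklists being kept. An exclusion count by criterion would be good reporting, but it would cover screened patients only and would not support statements about the clinic as a whole.
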